4.1.5.1 Efficacy Endpoints

RECIST 1.1 (24) will be used to assess response, duration of response (DOR) , and progression-free survival (PFS) ; Kaplan-Meier estimates will be generated for PFS, time-to-treatment failure, and overall survival (OS).

Exploratory analysis to assess survival endpoints, response and clinical benefit will be carried out also, using irRECIST,

irRECIST

irRECIST is RECIST 1.1 adapted as described below to account for the unique tumor response seen with immuno-therapeutics. irRECIST will be used by site investigators and local radiology review to assess tumor response and progression, and make treatment decisions. This data will be collected in the clinical database.

irRECIST will be used by the central imaging vendor, however, this evaluation will be done retrospectively. irRECIST takes into account the clinical condition/stability of subjects, as described in the Table below, in addition to response or progression via tumor imaging.

Clinically stable is defined by the following criteria:

- Absence of symptoms and signs indicating clinically significant progression of disease, including worsening of laboratory values
- No decline in ECOG performance status
- Absence of rapid progression of disease
- Absence of progressive tumor at critical anatomical sites (e.g., cord compression) requiring urgent alternative medical intervention

Table irRECIST: Tumor Imaging and Treatment after 1st Radiologic Evidence of PD **or** SD, CR or PR

	Clinically Stable		Clinically Unstable	
	Imaging	Treatment	Imaging	Treatment
1 st radiologic evidence of PD	Repeat imaging at \geq 4 weeks at site to confirm PD	May continue study treatment at the Investigator's discretion while awaiting confirmatory scan by site	Repeat imaging at \geq 4 weeks to confirm PD per physician discretion only	Discontinue treatment
Repeat scan confirms PD	No additional imaging required	Discontinue treatment (exception is possible upon consultation with Sponsor).	No additional imaging required	N/A
Repeat scan shows SD, PR or CR	Continue regularly scheduled imaging assessments	Continue study treatment at the Investigator's discretion	Continue regularly scheduled imaging assessments	May restart study treatment if condition has improved and/or clinically stable per Investigator's discretion. Next scan should occur according to the every 9 week (63 \pm 7 days) imaging schedule.

In determining whether or not the tumor burden has increased, decreased or stayed stable, site investigators should consider all target lesions as well as non-target lesions.

Any subject deemed **clinically unstable** should be discontinued from trial treatment at first evidence of progressive disease by tumor imaging and is not required to have repeat tumor imaging for confirmation.

For a **clinically stable** subject with first radiologic evidence of progressive disease (i.e., **unconfirmed progression of disease**), it is at the discretion of the site investigator to continue treating the subject with the assigned treatment per protocol until progression of disease is confirmed at least 28 days from the date of the tumor imaging first suggesting PD. If progression is not confirmed on the subsequent tumor imaging, the subject should continue to receive study therapy and have tumor imaging performed every 9 weeks (\pm 7 days) in the first year or every 12 weeks after the first year, or sooner if clinically indicated, to monitor disease status. If radiologic progression is confirmed by subsequent tumor imaging, then the subject will be discontinued from trial treatment.

NOTE: If a subject with confirmed progression by tumor imaging (i.e. 2 scans at least 28 days apart demonstrating progressive disease) is clinically stable or clinically improved, and there is no further increase in the tumor burden at the confirmatory scan, an exception may be considered to continue treatment upon consultation with the Sponsor.

4.1.5.2 Biomarker Research

Preliminary studies suggest that CD8 T cell infiltration and PD-L1 expression within tumors may predict efficacy for pembrolizumab, but definitive biomarkers are not yet available. To identify biomarkers to predict and/or follow efficacy for pembrolizumab in combination with other agents in metastatic breast cancer, we propose the following correlative studies to analyze the immune and stromal cells within metastatic tumors, as well as immune cells in peripheral blood, before and after therapy:

We will obtain archived biopsies or fresh biopsies as feasible of one or more metastatic lesion(s) before and one month post treatment. In addition, blood samples will be obtained at weeks 0, 2, 4, 6, 8, 10, 20, and 30 to track the temporal dynamics of the host immune response. Key questions we will address include:

1. Immune and stromal cells characteristics before treatment that correlate with clinical response.
2. Changes in immune and stromal cells after therapy that correlate with clinical response.

Approaches:

1. 12-color FACS analysis to enumerate/phenotype immune cell subsets and functional readouts, including cytokine production and signaling (phosflow)
2. TCR repertoire analysis via deep sequencing. Expansion of the T cell repertoire after therapy will be evidence for an immunological response and may indicate epitope spread.
3. Immunohistology using a novel quantitative, spatial image analysis system (Vectra, Perkin Elmer) that will enable us to analyze immune, stromal, and cancer cells in metastatic tumors via 8-color histology.
4. Gene expression analysis of stromal cells via RNA-Seq or microarrays.
5. Morphological / IHC TIL analysis of tumor biopsies.

Serial Cytokine Measurements

We will procure and analyze blood samples prior to initiating cycle one, and prior to cycle 2. The Human Cytokine Thirty-Plex Antibody Bead Kit (Invitrogen, Camarillo, CA) will be used according to manufacturer's instructions. The 30 cytokine panel includes: epidermal growth factor (EGF), eotaxin, basic fibroblast growth factor (FGF-basic), granulocyte colony-stimulating factor (G-CSF), granulocyte macrophage colony-stimulating factor (GM-CSF), hepatocyte growth factor (HGF), interferon alpha (IFN- α); IFN-gamma (γ), interleukin-1 beta (IL-1 β), interleukin-1 receptor antagonist (IL-1RA), IL-2; interleukin-2 receptor (IL-2R), IL-4, IL-5, IL-6, IL-7, IL-8, IL-10, IL-12p40/p70, IL-13, IL-15, IL-17, IFN- γ -inducible protein 10 (IP-10), monocyte chemoattractant protein-1 (MCP-1), monokine induced by IFN- γ (MIG), monocyte inflammatory protein-1 alpha (MIP-1 α), monocyte inflammatory protein-1 beta (MIP-1 β), regulated upon activation, normal T cell expressed

and secreted cytokine (RANTES), tumor necrosis factor (TNF)- α , and VEGF. Cytokine concentrations will be measured using the Bio-plex HTF Luminex instrument and results calculated using Bio-plex Manager 3.0 Software. The inter-assay precision for all cytokines is <10 % and the lower limit of quantitation is between 1 and 15 pg/ml, depending on the target. (25-29)

5.0 METHODOLOGY

5.1 Entry Criteria

5.1.1 Diagnosis/Condition for Entry into the Trial

Patients who are 18 years or older with 1) stage IV metastatic triple negative breast cancer (triple negative is defined as ER and PgR status is <1% of tumor cell nuclei are immunoreactive for ER or PgR, and HER2 status is FISH negative or IHC 0 or 1+) or 2) Stage IV HR+ HER2- (HR+) breast cancer (defined as ER or PgR $\geq 1\%$ of tumor cell nuclei are immunoreactive for ER or PgR and HER2 status is FISH negative or ICH 0 or 1+).

Subject Inclusion Criteria

In order to be eligible for participation in this trial, the subject must:

1. Be willing and able to provide written informed consent/assent for the trial.
2. Be ≥ 18 years of age on day of signing informed consent.
3. Have measurable disease based on RECIST 1.1.
4. Be willing to provide tissue from a newly obtained core or excisional biopsy of a tumor lesion. *Newly-obtained is defined as a specimen obtained up to 6 weeks (42 days) prior to initiation of treatment on Day 1. Subjects for whom newly-obtained samples cannot be provided (e.g. inaccessible or subject safety concern) may submit an archived specimen only upon agreement from the Sponsor.*
5. Have a performance status of 0 or 1 on the ECOG Performance Scale.
6. Demonstrate adequate organ function as defined in Table 1, all screening labs should be performed within 7 days of treatment initiation.

Table 1 Adequate Organ Function Laboratory Values

System	Laboratory Value
Hematological	
Absolute neutrophil count (ANC)	$\geq 1,500$ /mcL
Platelets	$\geq 100,000$ / mcL
Hemoglobin	≥ 9 g/dL or ≥ 5.6 mmol/L without transfusion or EPO dependency (within 7 days of assessment)
Renal	
Serum creatinine OR	≤ 1.5 X upper limit of normal (ULN) OR

Measured or calculated ^a creatinine clearance (GFR can also be used in place of creatinine or CrCl)	≥ 60 mL/min for subject with creatinine levels $> 1.5 \times$ institutional ULN
Cardiac	
Left ventricular ejection fraction by MUGA or Echocardiogram [#]	$\geq 55\%$; \geq upper limit of institutional normal
Hepatic	
Serum total bilirubin	$\leq 1.5 \times$ ULN OR Direct bilirubin \leq ULN for subjects with total bilirubin levels > 1.5 ULN
AST (SGOT) and ALT (SGPT)	$\leq 2.5 \times$ ULN OR $\leq 5 \times$ ULN for subjects with liver metastases
Albumin	> 2.5 mg/dL
Coagulation	
International Normalized Ratio (INR) or Prothrombin Time (PT)	$\leq 1.5 \times$ ULN unless subject is receiving anticoagulant therapy as long as PT or PTT is within therapeutic range of intended use of anticoagulants
Activated Partial Thromboplastin Time (aPTT)	$\leq 1.5 \times$ ULN unless subject is receiving anticoagulant therapy as long as PT or PTT is within therapeutic range of intended use of anticoagulants
Reproductive status for cohort 2: HR+ stage IV post-menopausal breast cancer	
Post-menopausal is defined by at least one of the following criteria:
 
Prior bilateral oophorectomy OR Amenorrheic for ≥ 12 months (if ≤ 55 years of age and prior chemotherapy or on medical ovarian ablative therapy or received ovarian radiation for ablation in the past 5 years and/or tamoxifen or an AI within the past year, then FSH and estradiol must be in the post-menopausal range and obtained within 28 days prior to registration) OR
 
Previous hysterectomy with one or both ovaries left in place (or previous hysterectomy in which documentation of bilateral oophorectomy is unavailable AND FSH values consistent with the institutional normal values for the post-menopausal state. FSH levels must be obtained within 28 days prior to registration).

^aCreatinine clearance should be calculated per institutional standard. [#] For patients with triple negative breast cancer [^] For patient with HR+ breast cancer
	

7. Female subject of childbearing potential should have a negative urine or serum pregnancy within 72 hours prior to receiving the first dose of study medication. If the urine test is positive or cannot be confirmed as negative, a serum pregnancy test will be required.
8. Female subjects of childbearing potential should be willing to use 2 methods of birth control or be surgically sterile, or abstain from heterosexual activity for the course of the study through 120 days after the last dose of study medication (Reference Section 5.7.2). Subjects of childbearing potential are those who have not been surgically sterilized or have not been free from menses for > 1 year.
9. Male subjects should agree to use an adequate method of contraception starting with the first dose of study therapy through 120 days after the last dose of study therapy.

10. Subjects currently on a bisphosphonate or denosumab are eligible for study therapy.

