5.1.2 Subject Exclusion Criteria

The subject must be excluded from participating in the trial if the subject:

1. Cohort 1: Has triple negative breast cancer, is considered for cohort 1 participation, and received prior anthracycline therapy.
Cohort 2: Has received prior aromatase inhibitor therapy and is deemed to be resistant to all three (anastrozole, letrozole, exemestane) approved AIs. Resistance is defined as progression within 12 months or while on an AI.
2. Patient is premenopausal (see Table 1, medical ovarian suppression is allowed)Is currently participating and receiving study therapy or has participated in a study of an investigational agent and received study therapy or used an investigational device within 4 weeks of the first dose of treatment.
3. Has a diagnosis of immunodeficiency or is receiving systemic steroid therapy or any other form of immunosuppressive therapy within 7 days prior to the first dose of trial treatment.
4. Has a known history of active TB (Bacillus Tuberculosis)
5. Hypersensitivity to pembrolizumab or any of its excipients.
6. Suboptimal cardiac function as defined by decreased left ventricular ejection fraction < 55% for cohort 1, and < 50% for cohort 2.
7. Prior pembrolizumab.
8. Has had a prior anti-cancer monoclonal antibody (mAb) within 4 weeks prior to study Day 1 or who has not recovered (i.e., \leq Grade 1 or at baseline) from adverse events due to agents administered more than 4 weeks earlier.
9. Has had prior chemotherapy, targeted small molecule therapy, or radiation therapy within 2 weeks prior to study Day 1 or who has not recovered (i.e., \leq Grade 1 or at baseline) from adverse events due to a previously administered agent.
 - Note: Subjects with \leq Grade 2 neuropathy are an exception to this criterion and may qualify for the study.

- Note: If subject received major surgery, they must have recovered adequately from the toxicity and/or complications from the intervention prior to starting therapy.

10. Has a known additional malignancy that has progressed or required active treatment in the past 5 years. Exceptions include basal cell carcinoma of the skin or squamous cell carcinoma of the skin that has undergone potentially curative therapy or in situ cervical cancer.

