5.2.4 Registration procedure

To register a participant, the subsequent procedure is to be followed.

1. The coordinator/research nurse should contact the DCC via telephone or email to provide notification regarding the pending registration and communicate desired timeline of the registration, especially if it must be completed promptly.

2. The coordinator/research nurse should then e-mail copies to [contact] of the following documents to the DCC:

- Completed Eligibility Criteria List (printed from Section 5.1.1 and 5.1.2 of the protocol)
- Source documentation to support eligibility criteria**
- Signed informed consent document
- Signed HIPAA authorization form (if separate from the informed consent document)
- Signed subject's Bill of Rights (COH only)

**For COH participants, provide copies of source documentation only if not readily available as a finalized record in the COH EMR.

3. After having received all documentation, the DCC will complete the review the documents to verify eligibility, working with the staff as needed to resolve any missing required source elements. A subject failing to meet all protocol eligibility requirements will not be registered.

4. Once eligibility has been confirmed, DCC staff will register the participant by assigning a participant study number and will enter the subject into the eCRF system, Medidata RAVE (once dosing is confirmed). The COH CRC will directly accession into MIDAS as per current policy and procedure.

5. Once registration has been completed, DCC staff will send a Confirmation of Registration Form, including the participant study number and cohort assignment to:

- the site study team: site PI, treating physician, biostatistician, protocol nurse, CRC and IDS pharmacy.

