7.1.2.7 Tumor Tissue Collection and Correlative Studies Blood Sampling

Laboratory Procedures/Assessments

Details regarding specific laboratory procedures/assessments to be performed in this trial are provided below Laboratory Safety Evaluations (Hematology, Chemistry and Urinalysis)

Laboratory tests for hematology, chemistry, urinalysis, and others are specified in Table 5.

Table 5 Laboratory Tests

Hematology	Chemistry	Urinalysis	Other
Hematocrit	Albumin	Blood	Serum β -human chorionic gonadotropin†
Hemoglobin	Alkaline phosphatase	Glucose	(β -hCG)†
Platelet count	Alanine aminotransferase (ALT)	Protein	PT (INR)
WBC (total and differential)	Aspartate aminotransferase (AST)	Specific gravity	aPTT
Red Blood Cell Count	Lactate dehydrogenase (LDH)	Microscopic exam (If abnormal)	Total triiodothyronine (T3)
Absolute Neutrophil Count	Carbon Dioxide ‡	results are noted	Free tyroxine (T4)
Absolute Lymphocyte Count	(CO_2 or bicarbonate)	Urine pregnancy test †	Thyroid stimulating hormone (TSH)
	Uric Acid		PK
	Calcium		
	Chloride		Blood for correlative studies
	Glucose		
	Phosphorus		
	Potassium		
	Sodium		
	Magnesium		
	Total Bilirubin		
	Direct Bilirubin		
	Total protein		
	Blood Urea Nitrogen		

† Perform on women of childbearing potential only. If urine pregnancy results cannot be confirmed as negative, a serum pregnancy test will be required.

‡ If considered standard of care in your region.

Laboratory tests for screening or entry into the Second Course Phase should be performed within 7 days prior to the first dose of treatment. After Cycle 1, pre-dose laboratory procedures can be conducted up to 72 hours prior to dosing. Results must be reviewed by the investigator or qualified designee and found to be acceptable prior to each dose of trial treatment.

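### As bracketed, the Cohort 2 post-menopausal definition requires FSH only when oophorectomy is undocumented, not when ovaries are known to remain after hysterectomy

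*Combined protocol and SAP*

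**What the plan says.** The row in Table 1 (Section 5.1.1) is headed "Reproductive status for cohort 2: HR+ stage IV post-menopausal breast cancer". It states that "Post-menopausal is defined by at least one of the following criteria" and lists three routes joined by OR.

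- **Route 1:** prior bilateral oophorectomy.
- **Route 2:** no menses for at least 12 months. For women aged 55 or under with certain prior treatments (chemotherapy, medical or radiation ovarian ablation, recent tamoxifen or an aromatase inhibitor), "then FSH and estradiol must be in the post-menopausal range and obtained within 28 days prior to registration".
- **Route 3:** "Previous hysterectomy with one or both ovaries left in place (or previous hysterectomy in which documentation of bilateral oophorectomy is unavailable AND FSH values consistent"; the reference for FSH is the institution's own post-menopausal range. It ends with the sentence "FSH levels must be obtained within 28 days prior to registration", after which the bracket closes.

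Exclusion 2 in Section 5.1.2 reads "Patient is premenopausal (see Table 1, medical ovarian suppression is allowed". Section 5.2.4 makes the registration document the "Completed Eligibility Criteria List (printed from Section 5.1.1 and 5.1.2 of the protocol", so the wording of these sections is what the coordinating center checks.

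**The concern.** The bracket in Route 3 opens before the undocumented-oophorectomy case and closes after the FSH timing sentence. Read as printed, FSH is asked of the woman who may have no ovaries and waived for the woman who certainly has at least one. No section gives a reason for that ordering.

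Two things are at stake. First, Cohort 2 is meant to be post-menopausal, and the rule, followed exactly, admits some women whose status has not been established. Second, two investigators could read the row differently, one testing every woman with a hysterectomy and another only those with missing records. In a 20-patient single-arm cohort judged on a response count, the definition of who is in the denominator should not depend on how a bracket is read.

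**Working it through.** **1. The logic of Route 3.** Let O be hysterectomy with one or both ovaries known to be in place, U hysterectomy with bilateral oophorectomy undocumented, and F a post-menopausal FSH within 28 days before registration.

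- As printed: Route 3 = O or (U and F).
- With the bracket closed after 'unavailable': Route 3 = (O or U) and F.

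| Woman | As printed | Bracket moved |
|---|---|---|
| O, FSH post-menopausal | qualifies | qualifies |
| O, FSH not post-menopausal or not measured | **qualifies** | does not qualify |
| U, FSH post-menopausal | qualifies | qualifies |
| U, FSH not post-menopausal or not measured | does not qualify | does not qualify |

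The two readings differ only in the second line. The brackets are balanced, one opening and one closing, so the printed reading does not depend on a missing character.

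**2. Does Route 2 catch her?** No. The routes are alternatives, so failing Route 2 does not matter once Route 3 is met. Take a woman aged 55 or under with recent tamoxifen: she needs FSH and estradiol under Route 2, yet enters untested under Route 3 if she has had a hysterectomy and her ovaries are known to remain.

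Route 2 is also a possible bypass once Route 3 is corrected. Hysterectomy itself stops menses, so after 12 months Route 2 is open to her. Its hormone test does not apply above age 55, or at 55 and under without the listed treatments.

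**3. Does another section catch her?**

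- Exclusion 2 (Section 5.1.2) points to Table 1 and adds no test.
- Exclusion 15 (Section 5.1.2) lets the investigator exclude for a confounding condition, but requires no test.
- The flow chart (Section 6.1) lists a pregnancy test and thyroid tests, with no FSH or estradiol.
- Table 5 (Section 7.1.2.7) lists β-hCG, T3, T4 and "Thyroid stimulating hormone (TSH"), again with no FSH or estradiol.
- Registration (Section 5.2.4) verifies source documents against the printed criteria, and so checks the rule as worded.

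**4. Illustrative size for the response rule.** Section 8.2.2 calls the combination worthy of further evaluation with 3 or more responses in 20. It states a type I error below 8% at a 5% response rate and power above 80% at 20%. Exact binomial values:

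- At 5%: 1 − (0.35849 + 0.37735 + 0.18868) = 0.0755, which agrees with the stated bound.
- At 20%: 1 − (0.01153 + 0.05765 + 0.13691) = 0.7939, just under the stated 80%. That small shortfall is separate from this point.

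Now suppose one of the 20 was admitted with working ovaries and the other 19 respond at 20%. For those 19, the probabilities of 0, 1 and 2 responses are 0.01441, 0.06846 and 0.15402, which sum to 0.23689.

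- If she cannot respond: 1 − 0.23689 = 0.763.
- If she responds at 5%: 1 − (0.23689 − 0.05 × 0.15402) = 1 − 0.22919 = 0.771.

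The loss is 2.3 to 3.1 percentage points. With two such patients the same calculation gives 74.6% (5% response) or 72.9% (no response). The count of patients and both response rates are assumptions; the documents give none of them.

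**The case against.** The strongest reply is that the intent is plain. The row heading says post-menopausal, exclusion 2 bars premenopausal patients, and the odd ordering looks like misplaced punctuation that a careful investigator would read through. An investigator who knows that the ovaries are working can exclude under exclusion 2, or under exclusion 15 as a confounder. Medical ovarian suppression is allowed, so such a woman need not be untreated in that respect. The group is also narrow: prior endocrine therapy, a hysterectomy, retained and functioning ovaries, and no suppression.

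Most of this stands, and it limits the consequence. It does not remove the defect. Both exclusions depend on the investigator already knowing or suspecting ovarian function, and the purpose of the FSH test is to find that out. Suppression is permitted but not required, and a woman labelled post-menopausal by Route 3 would not prompt the question.

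A reader might infer that no rule could stop such a woman, or that women with working ovaries will enter in numbers that damage the cohort's power. The documents support neither. Discretionary grounds for exclusion exist, no count or response rate is given, and on the assumptions above the effect can only lower the pass probability, so it would not produce a false positive.

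A reader might also infer that amenorrhea due to hysterectomy should simply be barred from Route 2. The protocol says nothing of the kind, and such a bar could conflict with exclusion 2's allowance for medical ovarian suppression.

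**Conclusion.** The point holds as a defect in an operative eligibility rule. As printed, Route 3 requires FSH only when bilateral oophorectomy is undocumented, so a woman with a hysterectomy and ovaries known to be in place is classed as post-menopausal without a hormone test. No other section requires that test of her under Route 3; only investigator discretion under exclusions 2 and 15 could intervene.

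This conclusion rests on the wording alone and needs no numerical assumption. The practical size is unknown and probably small. The fall from 79.4% to about 76–77% with one such patient is illustrative only: it assumes that she responds at 0% or 5% while all others respond at 20%. The planned sample size and decision rule need no change on this account.

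**What to change.** In Table 1, close the bracket after 'unavailable', so that the FSH condition and the 28-day window already in the row cover both hysterectomy cases. Make the same change in the eligibility checklist used at registration.

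The sponsor should then reconcile three passages so that they give one answer for a woman with a hysterectomy and retained ovaries: the 12-month amenorrhea route, the corrected hysterectomy route, and the allowance for medical ovarian suppression in exclusion 2. The aim is that the amenorrhea route does not bypass the FSH condition. How suppressed patients are handled is for the sponsor to state. If the printed reading was intended, the protocol should say so and give the reason.

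The cost is a one-line edit, a checklist update and a short clarification, plus an FSH test for the few women with a hysterectomy and retained ovaries. Some of them may no longer qualify.
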